#### 4.2.3 Nonclinical Safety Studies

Two hERG (human Ether-à-go-go Related Gene) assays were performed to assess effects of CT1812 on the rapidly activating delayed rectifier potassium channels (IKr) using channels stably transfected and over-expressed in Chinese Hamster Ovary cells. Using whole-cell patch clamp electrophysiology, CT1812 was tested in both studies in duplicate at concentrations of 1, 3, 10, and 30  $\mu\text{M}$ . Mean  $\text{IC}_{50}$  values of 26  $\mu\text{M}$  and 0.6  $\mu\text{M}$  were determined in the first and second assay, respectively. Reasons for the differing results are unknown. However, no ECG effects were noted in the telemeterized dog cardiovascular safety study or in the multiple-dose dog pivotal toxicology study when tested up to high-dose mean maximum plasma concentration ( $C_{\text{max}}$ ) values of approximately 4  $\mu\text{M}$ .

Safety pharmacology studies with rats revealed no apparent effects on (central nervous system (CNS) or pulmonary parameters following single oral dosages that exceeded the maximum tolerated dose in this species.

General toxicology studies with rats and dogs following oral dosing of CT1812 revealed dose-limiting toxicity that manifested as degenerative changes in the proximal tubules of kidney, hypercalcemia, and vascular mineralization and/or degeneration involving multiple tissues and

organs in each species. Tolerable and intolerable dosages and exposures, characterized with each species, informed the selection of dosages for this trial.

Genetic toxicology studies revealed no positive responses in bacterial and mammalian *in vitro* assays, or in an *in vivo* mouse bone marrow micronucleus assay when tested up to maximally feasible dosages.

### **4.3 Clinical Experience**

CT1812 has been administered safely with good tolerability in over 60 healthy volunteers in a placebo-controlled Phase 1a trial (COG0101). Six single and three multiple dose cohorts (QD, 14 days) were observed under close inpatient stay (N=6-8 treated, 2 placebo per cohort). Plasma concentrations of drug were shown to be approximately dose proportional across two orders of magnitude [0.13-14.93 mg (free base equivalent)/kg], and accumulation was minimal. Peak concentrations of CT1812 were reached within 1 to 2 hours and the plasma half-life was shown to be approximately 12 hours. Adverse events were mostly mild to moderate in severity and principally included headache, nausea, vomiting, diarrhea, constipation, abdominal pain, dyspepsia, upper respiratory tract infection, lightheadedness, syncope, myalgia, dizziness, rash and pain at the lumbar puncture site in those subjects who had lumbar punctures. There was only one AE of severe intensity, being an SAE of upper respiratory tract infection, occurring in one subject in the 840 mg dose of the multiple ascending dose (MAD) study, believed to be unrelated to study drug based on a similar pattern of URTIs in subjects receiving drugs other than CT1812 in the study unit during the same time period. One subject in the multiple dose cohort study developed a rash while on study drug. This subject showed improvement after discontinuing CT1812.

No evidence of renal toxicity has been observed to date based on routine measures of renal function (serum creatinine, blood urea nitrogen [BUN]) or cystatin C.

Four subjects in the MAD study showed an increase in liver function tests below 3X the upper limit of normal (including one subject on placebo). Subsequent studies will closely monitor liver enzyme parameters to determine if these were sporadic findings or possibly drug-related.

In COG0103 15 healthy volunteers evaluated potential effects of CT1812 on the disposition of sensitive substrates of selected CYP isoenzymes CYP2C19 (omeprazole), CYP2C9 (tolbutamide), CYP2D6 (dextromethorphan), and CYP3A4/5 (midazolam). Subjects were administered the probe drugs on Day -2 and pharmacokinetic (PK) evaluations performed. On Days 1 through 6, each subject took CT1812 560 mg. The CT1812 dose on Day 6 was taken

concomitantly with the probe drug cocktail, and PK evaluation was conducted. No significant interaction was observed for isoenzymes 2C19 and 2C9. A weak drug interaction was observed between steady-state CT1812 and midazolam 4 mg (CYP3A4). Midazolam area under the concentration-time curve ( $AUC_{last}$ ) and the  $AUC_{last}$  ratio (parent to metabolite) decreased by 24% and 28%, respectively, when midazolam 4 mg was taken with steady state CT1812 than when midazolam was taken alone. A weak drug interaction was observed between steady-state CT1812 and dextromethorphan 50 mg (CYP2D6), as indicated by a 1.75-fold and 2-fold increase in dextromethorphan  $AUC_{last}$  and  $C_{max}$ , respectively, following the combination treatment relative to dextromethorphan alone; however, the dextromethorphan/dextrorphan  $AUC_{last}$  ratio was similar between treatments. Based on the small magnitude of the interactions observed in this study for the isoenzymes CYP2D6 and CYP3A4, clinically meaningful implications are unlikely.

A Phase 1a/2 trial (COG 0102) has completed enrollment in Australia, evaluating the safety and pharmacokinetics of three doses of once a day CT1812 (90 mg, 280 mg, 560 mg) dosed for 28 days in subjects with mild to moderate Alzheimer's disease. This study enrolled 19 subjects in a 1:1:1:1 ratio of these doses vs. placebo. In general, all doses were relatively well tolerated, with no SAEs. All AEs were considered mild or moderate. While there was an increased frequency observed in total AEs with increasing dose, the small number of treated subjects does not permit definitive conclusions regarding the incidence of AEs by dose in a larger study population. Specific AEs which were noted to occur with greater frequency at the 560 mg dose included transient lymphocytopenia, nausea, vomiting, headache, fatigue, and depression. These AEs resolved in most instances while treatment was ongoing; one subject at the 560 mg dose experienced an ALT increase of 4.7 X ULN which resolved to normal levels after discontinuation of study drug. Cognitive outcomes were similar across the treatment groups. Plasma CT1812 concentration increased approximately dose proportionally, with a dose dependent increase in CSF concentration. CSF concentrations at all tested doses were > 80% of estimated brain PGRMC-1 receptor occupancy, which was the threshold associated with efficacy in preclinical studies.

#### **4.4 Rationale for Study**

This pilot trial project proposes to evaluate the effect of CT1812 on synaptic density and cognitive function in a Phase 1b randomized clinical trial in AD patients. By combining measurements of cognitive function with novel PET imaging of synaptic density in the same patients, this trial can directly test the mechanism of action of CT1812 and the A $\beta$  oligomer hypothesis of AD (Finnema et al., 2016). CT1812 is an orally administered lipophilic isoindoline, formulated as a fumarate salt, that is rapidly absorbed and highly brain penetrant. Cognition Therapeutics Inc. discovered

this mechanism of action along with the role of sigma-2/PGRMC1 in AD, as well as drug candidates that have the potential to rapidly restore synapses and improve symptoms and to attenuate clinical progression of the illness ( [REDACTED] ). Thus, the long-term development plan for these drug candidates includes pilot, early and late clinical development trials that evaluate the potential for both symptom improvement (months) and long-term disease modification (>year).

#### **4.5 Rationale for Selected Dose**

Based on brain receptor occupancy studies in animals, the daily dose of 300 mg/day is projected to exceed 95% occupancy while the 100 mg/day dose is projected to exceed 80% receptor occupancy. In the Phase 1 multiple dose 2-week trial, doses exceeding 300 mg/day were well-tolerated in both younger ( $\leq 64$  years of age) and older ( $\geq 65$  years of age) participants. In the phase 1 AD trial tolerability was also acceptable with no severe or serious adverse events observed at doses exceeding 300 mg/day.

## **5 STUDY OBJECTIVES**

### **5.1 Primary Objective**

- To evaluate the safety and tolerability of CT1812 in AD patients

### **5.2 Secondary Objectives**

- To evaluate the effect of CT1812 on brain synaptic density in AD patients using the SV2A PET ligand  $^{11}\text{C}$ -UCB-J.
- To evaluate the effect of CT1812 on cognitive and clinical outcomes in AD patients using the ADAS-Cog11 and ADAS-Cog13 (derived from ADAS-Cog14), NTB, ADCS-ADL, MMSE, CDR-SB, and ADCS-CGIC
- To evaluate the effect of CT1812 on brain activity in AD patients using FDG PET and resting state functional MRI
- To evaluate the effect of CT1812 on brain volume in AD patients using volumetric MRI
- To evaluate the effect of CT1812 on CSF pharmacodynamics in AD patients through measurement of CSF A $\beta$  40, A $\beta$  42, A $\beta$  oligomers, tau, phospho-tau, neurogranin, synaptosomal-associated protein-25 (SNAP25), synaptotagmin and NFL. Additional CSF biomarkers are listed in the statistical analysis plan.
- To evaluate the plasma and CSF concentrations of CT1812 in AD patients

### **5.3 Exploratory Objective**

- To correlate changes in synaptic density, other imaging endpoints and biomarkers, with cognitive function following CT1812 treatment.
- To evaluate the plasma CT1812 metabolites in AD patients

## **6 STUDY TYPE AND DESIGN**

### **6.1 Study Type**

This is a single-center, Phase 1b, randomized, double-blind, placebo-controlled, parallel-group trial in adults with mild to moderate AD.

### **6.2 Endpoints**

#### **6.2.1 Primary Endpoint**

Safety Endpoints

- The incidence and severity of adverse events (AE)
- The incidence of serious adverse events (SAE)
- Changes in vital signs
- Changes in physical and neurological exam findings
- Changes in body mass
- Changes in electrocardiogram (ECG) findings
- Changes in clinical laboratory testing (serum chemistry, hematology, urinalysis)
- Changes in the Columbia Suicide Severity Rating Scale (C-SSRS)

#### **6.2.2 Secondary Endpoints**

The primary imaging endpoint is the change from the baseline in synaptic density as measured by differences in SV2A PET ligand C-UCB-J uptake after dosing with CT1812 versus placebo.

Cognitive and clinical outcomes:

- Mini Mental State Exam (MMSE).

- Alzheimer's Disease Assessment Scale-Cognitive Subscale (ADAS-Cog) 11 and ADAS-Cog13 (delayed recall and Number Cancellation added to ADAS-Cog11 in the ADAS-Cog13); ADAS-Cog14 includes the maze added to ADAS-Cog13.
- Neuropsychological Test Battery (NTB) including Trails A and B, Digit Span, and Letter and Category Fluency (CFT).
- Alzheimer's Disease Cooperative Study (ADCS)-Clinical Global Impression of Change (CGIC).
- ADCS-Activities of Daily Living (ADCS-ADL).
- Clinical Dementia Rating Scale – Sum of Boxes (CDR-SB)
- Composite z-score scales (Cognitive Composite score; Memory composite score; Attention composite score; Executive Function composite score).
- Imaging Outcomes
  - FDG PET
  - Functional MRI
  - Volumetric MRI
- CSF pharmacodynamics in AD patients through measurement of CSF A $\beta$  40, A $\beta$  42, A $\beta$  oligomers, tau, phospho-tau, neurogranin, SNAP25, and NFL.

### **6.2.3 Pharmacokinetic Endpoints**

The following CT1812 pharmacokinetic assessments will be made based on serial pre-dose concentrations in plasma and CSF:

- CT1812 CSF/plasma concentration ratio
- Changes in pre-dose CT1812 plasma concentrations
- Plasma CT1812 metabolites

### **6.3 Study Design**

After consenting to participate in the study, screening procedures will occur between Days -60 and -1. Eligible participants will be randomized in a 1:1:1 (300 mg active: 100 mg active: placebo) ratio. The first dose of study drug will be administered in the clinic after all baseline procedures have been conducted. For the remainder of study days, participants will ingest study drug each morning at home. Participants and their study partners will return to the clinic for repeat psychometric/neurologic testing, safety studies, and PK and PD sample collection approximately every 2 weeks for the first 6 weeks and then every 3 weeks thereafter up to 24 weeks for the

[figure not shown]
primary study followed by an optional double-blind extension treatment period of an additional 24 weeks (337 days +/-2).as well as a follow up visit at 2 weeks after the final treatment visit.

Participants who prematurely discontinue the study for any reason will be asked to attend a final safety and efficacy visit.

## 6.4 Schematic Study Design

The study design schematic is shown in Figure 1.

**Figure 1 - Schematic Study Design**

## 7 STUDY DRUG

### 7.1 Supply and Storage

CT1812 will be provided to the site pharmacy as a hydroxypropyl methylcellulose (HPMC) capsule containing 191 mg or 64 mg mg of CT1812 fumarate salt (equivalent to 150 mg or 50 mg of the CT1812 free base, respectively). Study drug will be provided in amber colored, induction sealed, screw-top bottles with desiccant packs. All study drug (unopened and opened bottles) will be stored between 2-8 degrees Celsius.

Placebo capsules (containing of 191 mg or 64 mg of lactose monohydrate) will be supplied to match the CT1812 supplies in the same packaging and will require the same storage conditions (i.e., between 2-8 degrees Celsius).

Due to the short half-life, PET drugs are prepared and formulated immediately before administration, and therefore there are no issues with storage or stability. PET drug products are stored at room temperature and are stable for at least 60 min after preparation.

The preparation of sterile PET drug products is validated prior to human use. Sterility is achieved by passing the PET drug product through a 0.22 micron membrane filter during the last step of the formulation process. Prior to release for administration, a bubble point test is performed on the membrane filter used for terminal sterilization in order to validate and verify its integrity during the filtration process. Due to the short half-life, a sample of the PET drug product is tested for sterility after administration for further confirmation.

The level of endotoxin in each batch of the final PET drug product is determined quantitatively prior to release for administration using the Food and Drug Administration (FDA) approved Charles River Laboratory's Portable Testing System (Endosafe®-PTS).

The PET drug (radiotracer) will be prepared at the Yale PET Center in accordance with local Chemistry Manufacturing & Control (CMC) procedures and quality specifications described in local Drug Master File (DMF), both of which will be submitted to the FDA for approval. Briefly,  $^{11}\text{C}$ -UCB-J is radiolabeled by C- $^{11}\text{C}$  methylation of the boronate precursor with  $^{11}\text{C}$  methyl iodide ( $^{11}\text{C}$ MeI) according to the Suzuki cross-coupling method. The resulting PET drug is purified first by semi-preparative high pressure liquid chromatography (HPLC), and then followed by solid-phase extraction to remove the HPLC buffer mixture. Finally, the PET drug is formulated in <10% ethanolic saline solution (USP) containing <1% sodium bicarbonate (USP), and the resulting PET drug product is then passed through a 0.22 micron sterile membrane filter for terminal sterilization and collected in a sterile pyrogen free collection vial to afford a formulated I.V. solution ready for dispensing and administration.  $^{18}\text{F}$ -FDG:  $^{18}\text{F}$ -FDG will be administered immediately upon arrival at the PET center, or at most within 12 hours from the time of the end of synthesis (EOS). Based on the drug label,  $^{18}\text{F}$ -FDG can be stored at 25°C (77°F); excursions permitted to 15-30°C (59-86°F).

## **7.2 Packaging and Labeling**

The label on the bottles with CT1812 will contain the following information in the English language:

- Protocol number: COG0105
- Expiration date
- Lot number

- Contents
- Weight
- Storage conditions
- The sentence, “For Clinical Trial Use Only”
- Name of the Investigator
- Name, address and telephone number of the Sponsor

### **7.3 Administration**

CT1812 or matching placebo will be administered once each morning as a 300 mg or 100 mg oral dose (2 capsules). Capsules will be swallowed with ~240 mL of water. In order to ensure appropriate specimen collection times relative to dosing; on clinic days, participants will be asked to take their medication at the clinic upon the instruction of the site staff.

#### **7.3.1 Safety Stopping Rules**

The occurrence of any one of the following events will result in suspension of administration of study drug in all participants until safety information can be further reviewed by the Sponsor and Medical Monitor.

- Two occurrences of the same or similar SAE assessed as probably or possibly related to dosing with investigational product
- Two or more different participants with the same or similar severe AE assessed as probably or possibly related to dosing with the investigational product
- Four or more participants with the same or similar moderate AE which is possibly or probably related to dosing with investigational product

Under these circumstances, the Sponsor and Medical Monitor will review the available safety data and, in consultation with the study principal investigator, recommend whether dosing should continue, or if study drug administration should be terminated or dose reduced, or if additional monitoring procedures or safety precautions need to be employed.

If a stopping rule is achieved, selective unblinding of the participants involved may be performed by the Sponsor to determine if the SAEs/AEs are isolated to a single dose group or if they occurred in placebo participants.

The study or a dose group may also be terminated if the Medical Monitor, Study Director and Sponsor, in consultation with the lead principal investigator, determine that any adverse event(s) are occurring that are intolerable or pose a medically unacceptable safety risk.

#### **FOR INDIVIDUAL PARTICIPANTS:**

Participants who develop a severe adverse event or laboratory abnormality will not receive any additional doses and will be monitored until resolution of the AE or the return of laboratory abnormality to the acceptable screening value(s). Study drug may be re-initiated after consultation with medical monitor and sponsor. Any participant with:

- elevated ALT or AST greater than 5 X ULN should have dosing with study drug stopped and have laboratory tests repeated every 3-4 days until levels return to less than or equal to 1.5 X ULN. If the medical monitor and investigator are in agreement, study drug may be continued while a confirmatory ALT/AST is obtained within 3 days. If the confirmatory ALT/AST tests are below 5 X ULN, study drug may be continued. The frequency of the laboratory tests may be modified after discussion with the medical monitor if the liver enzymes are in a decreasing trend.
- Elevated ALT or AST greater than 3 X ULN in combination with total bilirubin > 2 X ULN or INR > 1.5 X ULN OR an ALT or AST > 3 X ULN with the appearance of fatigue, nausea, vomiting, right upper quadrant pain or tenderness, fever, rash, and/or eosinophilia (>5%) should have dosing with study drug stopped and have laboratory testing repeated every 3-4 days. If the medical monitor and investigator are in agreement, study drug may be continued while a confirmatory laboratory testing is obtained within 3 days. If these criteria are no longer met, study drug can be continued at the discretion of the medical monitor and investigator. The frequency of the laboratory tests may be modified after discussion with the medical monitor if the laboratory tests are trending towards normal.
- An increase in serum creatinine by 0.3 mg/dL (24.4 micromol/L) or 150% of baseline that is without clinical explanation of another etiology will result in repeated serum chemistry testing within 3-7 days. If the serum creatinine elevation is confirmed on repeated testing the study drug will be discontinued. If the serum creatinine elevation resolves upon

subsequent testing after study drug is discontinued the study drug may be restarted with serum creatinine monitoring at the discretion of the medical monitor and investigator.

- An increase in serum calcium to  $\geq 10.5$  mg/dL (2.63 mmol/L) that is without clinical explanation of another etiology will result in repeated serum chemistry testing within 3-7 days. If the serum calcium elevation is confirmed on repeated testing the study drug will be discontinued. If the serum calcium elevation resolves upon subsequent testing after study drug is discontinued the study drug may be restarted with serum calcium monitoring at the discretion of the medical monitor and investigator.
- Note: Fractional excretion of calcium will be monitored in each participant and interpreted in conjunction with serum creatinine and serum calcium. Given the ability of fractional excretion to fluctuate, no upper limit for discontinuing study drug based on fractional excretion of calcium has been set but it may be used as a stopping rule if persistent unexplained increases in fractional excretion of calcium are observed.

**Note:** Any unanticipated SAEs that are ‘related’ should be reported to the National Institute on Aging within 48 hours of knowledge of the same.

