5. DATA LISTINGS

5.1. Sources of Data

Data sets containing raw data will be provided by the Data Management group, extracted from the clinical study database of data entered into a Case Report Form. It is assumed that the database will contain the data from Screening through to the Follow-up Safety Visit of the study.

Analysis datasets will be generated from the data extracted from the study database, along with the following data entered separately or received from other sources:

- Randomisation/treatment assignment data, to be provided by the Avance unblinded statisticians
- Clinical laboratory safety data, to be provided by Quest Diagnostics to Avance Clinical data management
- CSF and plasma PK concentration data, to be provided by Agilex Biolabs
- PD concentration data (CSF) data, to be provided by Agilex Biolabs

All data entered into the CRF or provided from other sources as described above will be presented (explicitly or implicitly) in data listings or figures as described in Appendix 1. All available data collected for screen failed individuals will also be included in the individual data listings.

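### The creatinine stopping rule equates 0.3 mg/dL with 24.4 micromol/L (it is 26.5), and its percentage limb can be read two ways

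*Protocol*

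**What the plan says.** Protocol Section 7.3.1, in the rules for individual participants, sets the creatinine trigger as "An increase in serum creatinine by 0.3 mg/dL (24.4 micromol/L) or 150% of baseline that is without clinical explanation of another etiology". Meeting it leads to repeat chemistry within 3 to 7 days. The consequence of a confirmed rise is mandatory: "If the serum creatinine elevation is confirmed on repeated testing the study drug will be discontinued". Restart is possible if the elevation later resolves.

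The synopsis repeats the rule with the same figures, so neither place corrects the other. The SAP does not restate it.

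The calcium rule that follows in Section 7.3.1 has the same structure. It sets a level to be reached, 10.5 mg/dL, with its SI equivalent in parentheses: "mg/dL (2.63 mmol/L) that is without clinical explanation of another etiology".

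**The concern.** There are two separate points.

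- **Units.** The parenthetical SI figure should be the same threshold as 0.3 mg/dL, and it is not. The text does not say which figure governs. A rise that falls between them meets the rule on one figure and misses it on the other.
- **Relative limb.** The sentence speaks of an increase by an amount and then gives 150% of baseline as one of the amounts. Taken literally, that is a rise of 1.5 times baseline, to 2.5 times baseline. It can also be read as a rise to 1.5 times baseline. The calcium rule is worded as a rise to a level, so the list does not follow one convention.

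The rule decides whether a participant is retested and then taken off drug. It watches an organ that Sections 4.2.1 and 4.2.3 name as a site of dose-limiting toxicity in animals, in a trial whose primary objective is safety. It also bears on compliance. With no retest after a rise of 0.28 mg/dL, the site complies on the mg/dL figure and deviates on the SI figure. Section 18.1.2 requires deviations to be documented, and Section 18.1.3 rules out waivers.

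**Working it through.** **Inputs.** From Protocol Section 7.3.1: a rise of 0.3 mg/dL, its stated equivalent of 24.4 micromol/L, the 150% limb, and the calcium pair of 10.5 mg/dL and 2.63 mmol/L. Molar masses are not in the documents. Creatinine (C4H7N3O) is 113.12 g/mol from atomic weights, and calcium is 40.078 g/mol.

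**Step 1: convert the absolute limb.** The formula is micromol/L = mg/dL × 10,000 / molar mass, a factor of 10,000 / 113.12 = 88.40.

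- 0.3 × 88.40 = 26.52 micromol/L, against the printed 24.4.
- In reverse, 24.4 / 88.40 = 0.276 mg/dL.
- 24.4 / 26.52 = 0.920, so the printed figure is 8% low.

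**Step 2: try to reproduce 24.4.** It cannot be reproduced.

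- Conversion factors of 88, 88.4 and 88.42 give 26.4 to 26.5.
- The molar mass of creatine (131.13) gives 22.9, and that of creatinine hydrochloride (149.58) gives 20.1.
- Reaching 24.4 needs a factor of 24.4 / 0.3 = 81.3, that is, a molar mass of about 123.

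**Step 3: check the neighbouring rule.** For calcium, 10.5 mg/dL is 105 mg/L, and 105 / 40.078 = 2.620 mmol/L. The shortcut 10.5 / 4 gives 2.625. The printed 2.63 is within 0.4% of the first value and is the second value rounded. Loose rounding is therefore not the practice in this list.

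**Step 4: compare the readings of the relative limb.** For baseline b, whichever limb is met first sets the trigger: min(b + 0.3, k × b), with k = 1.5 or 2.5. The relative limb comes first when k × b < b + 0.3:

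- k = 1.5: 0.5b < 0.3, so b < 0.6 mg/dL.
- k = 2.5: 1.5b < 0.3, so b < 0.2 mg/dL.

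The baselines below are assumed examples, in mg/dL.

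| Baseline | Trigger, 1.5 × reading | Trigger, 2.5 × reading |
|---|---|---|
| 0.4 | 0.60 | 0.70 |
| 0.5 | 0.75 | 0.80 |
| 0.6 | 0.90 | 0.90 |
| 1.0 | 1.30 | 1.30 |

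At 0.6 mg/dL and above the readings agree. Below that, the 2.5 × reading is the less cautious one, and under it the relative limb is in effect inert.

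If the printed 24.4 micromol/L were applied, the trigger at a baseline of 1.0 would be 1.276 mg/dL under either reading. The point below which the readings part would move to 0.276 / 0.5 = 0.55 mg/dL.

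**The case against.** The strongest reply concedes the arithmetic and disputes the weight.

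- The mg/dL figure comes first in both the creatinine and the calcium rule, so a reader would take it as governing and the SI value as a misprinted equivalent. With the rounded factor 88 the equivalent is 26.4, one digit away from 24.4.
- The trial has one centre and one named safety laboratory (SAP Section 5.1), so sites using different units cannot conflict. If the laboratory reports mg/dL, the SI figure may never be used. Even if staff did use it, only rises of exactly 0.28 or 0.29 mg/dL would be affected at two-decimal reporting, and none at one decimal.
- The error is cautious, and a confirmatory test precedes discontinuation. Chemistry is drawn at every scheduled on-treatment visit, and the safety committee receives laboratory reports every two weeks (Section 15.1.1).
- The two readings of the relative limb agree at all baselines of 0.6 mg/dL or more, and the documents give no baseline creatinine distribution to show that anyone falls below that. The 0.3 mg/dL limb protects every participant under either reading.

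Most of this stands as a limit on the size of the effect. It does not make the figures agree. The misprint explanation is plausible but is an inference, the laboratory's reporting unit is not stated, and nothing in either document says which figure controls. The visible eligibility text in Section 9.3 excludes poor renal function but sets no lower limit on creatinine, so low baselines are possible. The relative limb is properly the secondary point.

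**Conclusion.** The concern holds. The SI value is wrong as written in both places: it should be 26.5 micromol/L, and the printed 24.4 is 8% low. The error affects only rises from 0.276 to just under 0.300 mg/dL and leads to earlier action. At worst it causes an unnecessary retest, or a stop on a confirmed rise slightly below the intended threshold. With about 7 participants per arm, one avoidable discontinuation would be noticeable, but the confirmatory test and the option to restart make a lasting loss unlikely.

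The relative limb is ambiguous, with a consequence only at baselines below 0.6 mg/dL. The trigger differs by 0.05 mg/dL at an assumed baseline of 0.5 and by 0.10 mg/dL at an assumed baseline of 0.4.

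These conclusions assume that 0.3 mg/dL is the intended value and that 'or' means whichever limb is met first. No analysis in the SAP changes. The case for correcting it rests on the kind of text this is, a mandatory stopping threshold for a known target organ, and not on the number of participants likely to be affected.

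**What to change.** The sponsor should first confirm that 0.3 mg/dL and 1.5 times baseline are the intended values. Then, in both Section 7.3.1 and the synopsis, replace the opening of the rule with: a rise in serum creatinine of at least 0.3 mg/dL (26.5 micromol/L) above baseline, or a value of at least 1.5 × baseline. The rest of the rule can stay as it is.

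The cost is one line in each of two places in the next protocol amendment. Data collection and analysis do not change.
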